A study involving 119 healthy subjects investigated the combination of tES intervention with retrieval practice and found that the strong retrieval practice effect left no room for tES to improve memory performance[7]. The combination of single-session online tES with retrieval practice in healthy individuals and found that the memory performance of anodal stimulation was inferior to cathodal stimulation and sham stimulation [8]. We have already explored the role of continuous periodic tES combined with interim testing on spatial route learning in patients with schizophrenia in a previous study [9], and found that both the learning strategy and tES independently facilitated the ability of patients with schizophrenia to learn new information in spatial route learning, suggesting that the tES of L-DLPFC has a significant improvement effect. In contrast, targeted tES treatment may be more effective for memoryimpaired populations such as schizophrenia [10]. Therefore, further investigation is needed to determine the effectiveness of combining tES and retrieval practice for semantic memory intervention in schizophrenia patients. From a theoretical perspective, this combination may have a dual activation effect because (1) tES stimulation can enhance activation levels of the L-DLPFC, improving its cognitive function impairment; (2) retrieval practice can not only help patients initiate semantic memory strategies and promote semantic elaboration but also actively activate the brain regions stimulated by tES, thereby producing a synergistic effect.

Therefore, this study aims to investigate whether combining tDCS, tACS with retrieval practice facilitates the maintenance of semantic memory and improvement of semantic organization by comparing the use of retrieval practice strategies in patients receiving anodal L-DLPFC stimulation, sham stimulation.

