#### 2. Methods

#### 2.1 Participants

60 schizophrenic patients plan to be recruited from the mental health center. All patients must sign an informed consent form.

Patients with schizophrenia are diagnosed and assessed by two chief psychiatrists. Neuropsychological background tests included the Montreal Cognitive Assessment (MoCA)[11] for general cognitive function and the Positive and Negative Syndrome Scale (PANSS)[12]. A parallel-group, single-blind study design was used to assign subjects to the two stimulus types using a stratified randomization method based on baseline Montreal Cognitive Assessment performance. The characteristics of the participants are presented in Table 1, showing no significant differences in participant characteristics between the two stimulation types groups.

Patients with schizophrenia were included based on the following criteria: (1) meeting the diagnostic criteria for schizophrenia according to the Diagnostic and Statistical Manual of Mental Disorders, Fifth Edition (DSM-5); (2) aged 18 years or older, regardless of gender, with an educational level of elementary school or above; (3) all patients received stable-level antipsychotic medication treatment, were in a stable phase of disease treatment, able to understand the testing requirements, and cooperated to complete all research tasks; (4) no history of neurological disorders or other serious physical illnesses, and no history of intellectual disability; (5) no color blindness, color weakness, or other color vision impairments, with normal vision or corrected vision.

Exclusion criteria were as follows: (1) clear cognitive impairment caused by somatic or cerebral organic lesions, such as cerebrovascular diseases, traumatic brain injury, etc; (2) individuals with mental disorders caused by substance dependence or abuse, or the use of psychoactive substances; (3) history of brain injury or other central nervous system-related organic diseases; (4) individuals at significant risk of suicide or harming others; (5) participation in similar experiments in the past 30 days prior to baseline.

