#### 2.2 Design

A mixed experimental design of 3 (Stimulation type: tES stimulation, tACS stimulation, sham stimulation)  $\times$  2 (Learning strategy: retrieval practice, restudy)  $\times$  2 (Retention interval: Immediate recall, Delayed recall) was employed. Stimulation type was a between-subjects variable, while learning strategy and testing time were within-subject variables. The dependent variables were the correct recall rate and Adjusted Ratio of Clustering (ARC) scores in the testing phase.

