#### (1) Stimulation phase

In the tDCS group, the anode was placed over the left DLPFC (F3), and the cathode was placed over the contralateral supraorbital area (FP2). A direct current of 2mA was applied for 20 minutes during each stimulation session. In the tACS group, the anode was placed in the F3 region of the left dorsolateral prefrontal cortex (DLPFC), and the cathode was placed in the right supraorbital region (Fp2), and the current used was 2 mA AC at 40 Hz, with a stimulation time of 20 min. In the sham group, the stimulation parameters, including the stimulation site and duration, were identical to those of the anodal group. However, during the 10-second ramp-up and ramp-down periods before and after stimulation, patients were unaware that the current was turned off.

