#### 2.5 Date scoring & analysis

The experimental results were processed using SPSS 26.0. The correct recall rate of word lists was calculated for each subject by the experimental assistant. Then, Free recall organization was measured by the Adjusted Ratio of Clustering (ARC) scores [14,15]. ARC scores range from 1 to 1. A 0 score indicates a level of clustering similar to what would be expected by chance, and a score of 1 implies perfect clustering. Negative values of ARC scores mean atypical and uninterpretable recall patterns[16]. For that reason, negative scores were excluded from analyses.

A mixed-design analysis of variance (ANOVA) was conducted to compare the correct recall rates and ARC clustering scores between the two learning strategies under two stimulation conditions. All statistical tests were performed at a significance level of 0.05, and post-hoc comparisons were adjusted using Bonferroni correction. Effect sizes were reported using partial eta-squared ( $\eta_p^2$ ; ANOVAs).

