# List of abbreviations

tES transcranial electrical stimulation

L-DLPFC left dorsolateral prefrontal cortex

**VLPFC** ventrolateral prefrontal cortex

ARC Adjusted Ratio of Clustering

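### The protocol describes three stimulation arms in its design and procedure but writes the randomisation, the baseline comparison and the ANOVA for two

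*Protocol*

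**What the plan says.** Two places in the protocol describe three arms:

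- Section 2.2 (Design) lists the levels of the between-subjects factor as "Stimulation type: tES stimulation, tACS stimulation, sham stimulation".
- Section 2.4, Stimulation phase, describes a tDCS group, a tACS group ("In the tACS group, the anode was placed in the F3 region") and a sham group.

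Three places describe two:

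- Section 2.1, randomisation: the plan is to "assign subjects to the two stimulus types using a stratified randomization method".
- Section 2.1, baseline: Table 1 is described as "showing no significant differences in participant characteristics between the two stimulation types groups".
- Section 2.5, analysis: the mixed ANOVA is to "compare the correct recall rates and ARC clustering scores between the two learning strategies under two stimulation conditions".

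Two further places are ambiguous. The aim at the end of section 1 names both tDCS and tACS, but then describes the comparison as "comparing the use of retrieval practice strategies in patients receiving anodal L-DLPFC stimulation, sham stimulation". The sham parameters in section 2.4 are "identical to those of the anodal group", in the singular, although both active groups are described with an anode at F3.

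The arm names also differ. The direct-current arm is called tES in section 2.2 and tDCS in section 2.4, while the abbreviation list gives "tES transcranial electrical stimulation", a term that also covers tACS.

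**The concern.** The number of arms fixes how patients are allocated, how many levels the stimulation factor has in the model, and how many post-hoc pairs the Bonferroni rule in section 2.5 must cover. The two-arm wording stands in the two operative steps, randomisation and analysis. Someone working from those sentences would leave one arm unallocated, leave one out of the analysis, or combine the two active arms. In each case the separate evaluation of tDCS and tACS that sections 2.2 and 2.4 set up is lost. If the conflict is still open once data exist, the choice between separate, combined or omitted arms becomes a data-dependent one.

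**Working it through.** **Arm count by section**

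| Place in the protocol | Arms |
|---|---|
| 2.2 Design, factor definition | 3 |
| 2.4 Stimulation phase, group procedures | 3 |
| 2.1 Randomisation | 2 |
| 2.1 Baseline comparison | 2 |
| 2.5 ANOVA | 2 |
| 1 Aim | mixed: two active methods named, then anodal and sham compared |

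Could the two types mean active versus sham, or two active types with sham as an uncounted control? Section 2.2 speaks against both, because its stimulation-type factor counts sham as one of three levels. No section says that the active arms are combined.

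**What the choice changes**

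Inputs from the protocol: 60 patients (section 2.1); significance level 0.05 with Bonferroni-adjusted post-hoc comparisons (section 2.5). The protocol gives no allocation ratio, effect size, SD or power, so there is no figure of its own to reproduce. Assumptions made here: equal allocation, two-sided tests, 80% power.

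- Patients per arm: 60/2 = 30, or 60/3 = 20.
- Degrees of freedom for stimulation: 2 − 1 = 1 (error 60 − 2 = 58), or 3 − 1 = 2 (error 60 − 3 = 57).
- Pairwise comparisons: 1, or 3 × 2/2 = 3. Bonferroni level: 0.05, or 0.05/3 = 0.0167.

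The detectable standardised difference is approximately d = (z for 1 − α/2 + z for 0.80) × √(1/n₁ + 1/n₂):

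- 30 vs 30, α = 0.05: (1.960 + 0.842) × √(2/30) = 0.72.
- 20 vs 20, α = 0.0167: (2.394 + 0.842) × √(2/20) = 1.02.

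The noncentral t distribution, which suits these sample sizes better, gives:

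| Reading | Groups compared | α | Detectable d |
|---|---|---|---|
| Third arm never allocated | 30 vs 30 | 0.05 | 0.74 |
| One of three arms left out of the analysis (20/60 = 33% unanalysed) | 20 vs 20 | 0.05 | 0.91 |
| Active arms combined | 40 vs 20 | 0.05 | 0.78 |
| Three arms kept, all pairs compared | 20 vs 20 | 0.0167 | 1.06 |

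The rise from 0.91 to 1.06 comes from the Bonferroni level alone, since both rows compare 20 with 20.

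Combining the active arms has a further cost. If one works with effect d and the other not at all, the combined contrast estimates (d + 0)/2. With an assumed d = 0.8 this is 0.4, and the power of 40 vs 20 at 0.05 is about 30%.

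These figures are for a difference between arms on a single measure. They do not apply to the interaction of stimulation with learning strategy or retention interval.

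**The case against.** The strongest reply is that the intention can be recovered. Section 2.2 is the only formal definition of the factor and section 2.4 gives each of three groups its own procedure, so the most coherent reading is three arms with counts left uncorrected elsewhere. No section mentions combining or dropping an arm. That is fair, and it makes three arms the likelier intention. It does not settle the matter: the two-arm count appears in three separate statements, including the ones that govern allocation and analysis.

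Several supporting points are indeed weaker. The baseline sentence describes a result and instructs nobody. Anodal in the aim could cover both active groups. Both active groups share the F3/Fp2 placement and 20 minutes, so for site and duration the sham match is the same whichever is meant. The tES label beside tACS in section 2.2 can only mean tDCS. These are signs of loose wording, and the finding does not rest on them.

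The ANOVA sentence also does not name retention interval, but section 2.2 does, and full model detail may belong in a statistical analysis plan that is not shown. This is therefore no more than a side remark. A statistical analysis plan could specify contrasts, but it would not remove a contradiction inside the protocol about how many groups patients are randomised to.

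The power figures rest on assumptions and a simplified test. They illustrate the consequence and carry no weight in the conclusion.

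**Conclusion.** The concern holds and must be fixed. Sections 2.2 and 2.4 describe three arms; the randomisation in section 2.1 and the ANOVA in section 2.5 are written for two; nothing reconciles them. This follows from the text alone, with high confidence. Its practical size, for 60 patients and assumed equal allocation, is a third fewer patients per arm under three arms than under two (20 against 30), and three adjusted comparisons in place of one. Under the two-condition text, the effects of tDCS and tACS cannot be told apart.

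**What to change.** Before enrolment, bring the aim in section 1 and sections 2.1, 2.2, 2.4 and 2.5 to one number of arms and one set of arm names, keeping tES as the umbrella term only. Which number is intended is for the sponsor to state.

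- **If three arms:** in section 2.1, state randomisation to tDCS, tACS and sham with the allocation ratio, and describe baseline across three groups. In the aim, name all three in the comparison. In section 2.4, say which group or groups the sham parameters are matched to. In section 2.5, specify the 3 (tDCS, tACS, sham) x 2 (learning strategy) x 2 (retention interval) mixed ANOVA for both recall rate and ARC score, with Bonferroni-adjusted comparisons among the three arms.
- **If two arms:** correct the aim and sections 2.2 and 2.4 to match.

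The cost is wording only, with no additional patients, and the protocol gives its status as not yet recruiting. If three arms are confirmed, the sponsor should recognise that, with equal allocation, each pairwise comparison rests on about 20 patients per arm.

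### The aim is active stimulation versus sham, but section 2.5 names no sham contrast; with three arms and the usual three-pair Bonferroni family, this costs about 3 to 8 points of power

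*Protocol*

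**What the plan says.** The aim, at the end of the Protocol's Introduction, names tDCS and tACS as the modalities to be combined with retrieval practice. It is to be met by "comparing the use of retrieval practice strategies in patients receiving anodal L-DLPFC stimulation, sham stimulation". No comparison of tDCS with tACS is asked for.

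Section 2.2 makes stimulation a between-subjects factor with three levels: "3 (Stimulation type: tES stimulation, tACS stimulation, sham stimulation". The stimulation phase in section 2.4 likewise describes a tDCS, a tACS and a sham group. Section 2.1, however, says that patients are randomised to two types ("assign subjects to the two stimulus types using a stratified randomization method"), and section 2.5 describes the ANOVA as a comparison "between the two learning strategies under two stimulation conditions".

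On inference, section 2.5 gives a mixed-design ANOVA, the level ("All statistical tests were performed at a significance level of 0.05") and the adjustment ("post-hoc comparisons were adjusted using Bonferroni correction"). It does not say which comparisons form the Bonferroni family, or whether they are run only after a significant F test. On size, section 2.1 says "60 schizophrenic patients plan to be recruited from the mental health center". No allocation ratio, effect size, SD or power is given.

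**The concern.** With three arms, the ANOVA's stimulation test and its stimulation-by-strategy test each have 2 degrees of freedom. A significant result says that some arm differs, not that tDCS or tACS differs from sham. The answer to the stated aim is then left to the post-hoc step. If that step covers all three pairs, the two comparisons of interest share the error rate with tDCS versus tACS, which the aim does not raise.

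The Introduction's argument for synergy is a still more specific question: is the gain from retrieval practice over restudy larger under active stimulation than under sham? That is one single-degree-of-freedom contrast per active arm, and section 2.5 does not name it.

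At stake is some power on the comparison the trial exists to make, and the chance of a significant overall stimulation effect with neither sham comparison passing.

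**Working it through.** The Protocol states no power figure, so there is nothing to reproduce. The check compares two rules for the same 60 patients.

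**Inputs**
- Total 60 (section 2.1); three arms (section 2.2); level 0.05 (section 2.5).
- Assumed, because not stated: equal allocation, so 60 / 3 = 20 per arm and 60 − 3 = 57 error degrees of freedom; two-sided tests; true differences d from 0.4 to 1.2 SD.

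**Critical values at 57 df**
- Bonferroni over three pairs: 0.05 / 3 = 0.0167 per comparison, |t| > 2.467.
- Bonferroni over the two sham pairs: 0.05 / 2 = 0.025 per comparison, |t| > 2.302.
- Dunnett for two contrasts sharing the sham arm (correlation 0.5): |t| > 2.27, about 0.027 per contrast.

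**Power for one active-versus-sham comparison.** With SD 1, the standard error is √(2/20) = 0.316, so the noncentrality is d / 0.316. At d = 0.8 it is 0.8 / 0.316 = 2.53, and the noncentral t distribution gives 52.9% above 2.467, against about 60.5% above 2.27.

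Simulation of three arms of 20 (200,000 trials per scenario), both active arms effective, in percent. The first column also requires a significant F test.

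| d (SD) | F, then Bonferroni-3 | Bonferroni-2 | Dunnett | Dunnett minus first column | Dunnett minus Bonferroni-2 |
|---|---|---|---|---|---|
| 0.4 | 12.1 | 15.7 | 16.6 | 4.5 | 0.9 |
| 0.5 | 19.5 | 24.4 | 25.5 | 6.0 | 1.1 |
| 0.6 | 29.0 | 35.0 | 36.3 | 7.3 | 1.3 |
| 0.7 | 40.5 | 46.9 | 48.3 | 7.8 | 1.4 |
| 0.8 | 52.7 | 59.2 | 60.5 | 7.8 | 1.3 |
| 0.9 | 64.8 | 70.7 | 71.9 | 7.1 | 1.2 |
| 1.0 | 75.3 | 80.1 | 81.1 | 5.8 | 1.0 |
| 1.2 | 90.5 | 92.9 | 93.4 | 2.9 | 0.5 |

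The gains are almost unchanged if the other active arm has no effect or half the effect.

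**Where the loss comes from.** Dropping the F-test requirement but keeping three pairs moves power from 52.7% to 52.9% at d = 0.8. The largest cost of that requirement in any scenario is about 0.5 point (52.5% against 53.0% at d = 0.8 with the other arm at half effect). Almost all the loss is therefore the family of three instead of two.

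**Targeting.** If only tDCS works, at 0.8 SD, F is significant in 72.5% of trials. In 53.6% it is significant and at least one sham comparison passes Bonferroni-3. In 72.5 − 53.6 = 18.9% of trials F is significant with neither sham comparison passing. In most of these the pair that passes is tDCS versus tACS.

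**Synergy contrast.** The same table applies if d is read in SDs of the within-patient retrieval-minus-restudy difference. The Protocol gives no basis for judging which d is plausible on that scale.

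**The case against.** The strongest objection is that section 2.5 does not prescribe the rule being criticised. A reader might infer from it that all three pairs are tested, and only after a significant F test. Neither is written there. If the sponsor means the two sham pairs, the stated Bonferroni rule already gives 0.025 each, and moving to Dunnett gains about 1 point. This stands, and it makes the size conditional. It does not remove the point: three pairs is the natural family for unrestricted post-hoc tests of a three-level factor, and nothing in section 2.5 narrows it.

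Second, the comparison family can be left to a statistical analysis plan. That is true of the detail, but section 2.5 does fix a method, and the method does not address the aim directly.

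Third, section 2.5 read literally has two stimulation conditions, hence a single-degree-of-freedom test with no pairwise penalty. This also stands. The contradiction with section 2.2 has to be resolved first, and the power figures hold only for three arms.

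Fourth, contrasts on mean recall alone would serve the aim poorly, since it concerns retention and semantic organisation. This is correct, so the contrasts must also cover ARC and delayed recall.

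**Conclusion.** The point holds as a cheap improvement. With three arms, 20 patients each, two-sided 0.05 and a three-pair Bonferroni family, the plan gives up about 3 to 8 points of power per active-versus-sham comparison over 0.4 to 1.2 SD, and about 6 to 8 points over 0.5 to 1.0 SD. Requiring a significant F test accounts for at most about 0.5 point of this. With a family of the two sham pairs, the loss is about 1 point.

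Two stronger readings are not supported. A reader might infer that the analysis is invalid; it is not, because Bonferroni over the pairs controls their type I error. A reader might also take 6 to 8 points as a property of this trial; the Protocol gives no effect size, SD or allocation ratio, so that range is conditional on the assumptions above. Nor does the change rescue a small effect: at 0.5 SD, power is 19.5% under one rule and 25.5% under the other.

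**What to change.** 1. Make sections 2.1, 2.2 and 2.5 agree on the number of stimulation arms, and state the allocation ratio.
2. If there are three arms, prespecify two Dunnett-adjusted contrasts in section 2.5, tDCS minus sham and tACS minus sham, for both recall rate and ARC.
3. Apply them to the retrieval-minus-restudy difference (the synergy question) and to the overall stimulation effect. Include delayed recall, which carries the question of maintenance.
4. State which single outcome, time point and effect is primary. Each Dunnett adjustment covers only its own pair of contrasts, so without this the separate families would go unadjusted against one another.
5. Report tDCS minus tACS descriptively, with a confidence interval.

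The cost is a change of wording in the analysis section and no additional patients; the Protocol's status section lists the study as not yet recruiting. The downside is that there is no confirmatory tDCS-versus-tACS test, which the stated aim does not ask for. A sponsor who does want that test should say so in the aim and keep the three-pair family.

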## **Study Status**

**Record Verification: August 2024** 

**Overall Status: Not yet recruiting** 

Study Start: August 12, 2024 [Anticipated]

Primary Completion: September 15, 2024 [Anticipated]

Study Completion: September 20, 2024 [Anticipated]

# List of abbreviations

tES transcranial electrical stimulation

L-DLPFC left dorsolateral prefrontal cortex

**VLPFC** ventrolateral prefrontal cortex

ARC Adjusted Ratio of Clustering

